# **Study Protocol, Statistical Analysis Plan, and Informed Consent for**

## **Utilization of Hepatitis C Positive Kidneys in Negative Recipients**

### **(USE-Hep C)**

#### **I. Objectives**

To evaluate the safety and feasibility of transplanting kidneys from Hepatitis C virus (HCV) infected donors into recipients without HCV infection

#### **II. Background and Rationale**

##### **a. Background**

Patients with end stage renal disease (ESRD) have increased mortality compared to their healthy peers with a five years survival chance of 42-52% in hemodialysis and peritoneal dialysis patients respectively. Over the last decade, the number of ESRD patients has risen significantly. In 2015, there was over 124,000 new cases and 703,243 prevalent cases of ESRD in the United States (1a). Kidney transplantation remains the preferred treatment modality. Successful kidney transplantation is associated with improved survival, improved quality of life and health care cost savings when compared to dialysis. However, the gap between patients in needs and available organs remains large. In 2017, there were over 94,000 patients waiting on the deceased donor kidney transplant waiting list with only 28,588 deceased donor transplantation performed(1). This organ shortage along with the advances in the available treatments of transmittable diseases such as human immunodeficiency virus (HIV) and hepatitis C virus (HCV) has prompted the transplant society to explore donors previously believed to be an acceptable candidate for donation.

Traditionally, HCV donor positive (HCV D+) kidneys were offered only to HCV positive recipients due to a 100% HCV transmission risk. Due to the low numbers of kidney transplant candidates who are also HCV positive, many of these kidneys are discarded. The development of direct acting anti-viral drugs (DAAs) have transformed the realm of HCV therapy. DAAs has turned HCV hepatitis into a highly curable condition with cure rates exceeding 95% for all different HCV genotypes 1 through 6(2-6).

DAAs can be safely used in all solid organ transplantation. Sofosbuvir/velpastasvir (Epclusa) combination was used for treatment of recurrent HCV infection (genotype 1 through 6) after liver transplantation (3, 5, 7). A 12 weeks treatment resulted in overall 96% cure rate in patients with and without cirrhosis. The drug combination was very well tolerated and had minimal interaction with immunosuppressants. Once daily Glecaprevir/pibrentasvir (Mavyret) combination was used to treat HCV infection (genotype 1 through 6) in 80 liver transplant and 20 kidney transplant recipients in the MAGELLAN-2 study(8). The overall cure rate was 98% at 12 weeks post-treatment. The drug combination was again very well tolerated.

These advances in the treatment of HCV infection has made it possible to entrain the use of organs from HCV viremic patients into non infected HCV recipients with plan for HCV treatment post transplantation

**b. Rationale:**

DAs are highly tolerated by patients and carry a cure rate of >95%. This favorable side effect profile and high efficacy can help expand the pool of available organs by increasing the utilization of organs from HCV infected donors. Over the past decade, the opioid crisis have increased the number of HCV infected deceased donors. These donors are usually young with fewer comorbid conditions such as diabetes and hypertension. Organ procured from such donors are usually of good quality. The transmission rate of HCV when using infected organ is guaranteed but the availability of DAs make this less of a concern. This scenario has been tested and proven safe by other groups. The EXPANDER (Exploring Renal Transplant Using Hepatitis C Infected Donors for HCV- Negative Recipients) group at Johns Hopkins University performed transplantation of kidneys from HCV+ into 10 HCV- recipients(9). The group used **elbasvir-grzoprevir** (supplemented with sofosbuvir for genotype 2, 3) started before transplant and continued for 12 weeks post-transplant. There were no treatment related adverse effects. HCV virus was undetectable with stable liver function in all recipients 12 weeks after completion of treatment.

Another group, the THINKER (Transplanting Hepatitis C kidneys Into Negative Kidney Recipient), from the University of Pennsylvania also used similar drug combination elbasvir-grazoprevir (Zepatier) in 20 HCV negative recipients who received kidneys from donor infected with HCV genotype -1(10). The group reported a 100% transmission rate of HCV with 100% cure rate as evident by undetectable HCV pcr in the blood 12 weeks post treatment. There were again no treatment related adverse events. Kidney allograft function was excellent at 6 and 12 months.

The use of HCV + donors into negative recipients has also been investigated in thoracic organ transplantation including heart (11) and lung (12, 13). Patients in these reports were treated by either Sofosbuvir/Ledipasvir (Harvoni) if they contacted HCV genotype 1 or Sofosbuvir/Velpatasvir if they contracted other genotypes. All of the reported cases had complete cure of HCV transmitted after transplant and no treatment associated adverse effects.

Giving the large body of evidence supporting the safety and efficacy of DAs in treatment of HCV in the transplant recipients, we at the Ohio State University, would also like to explore the safety of transplanting HCV positive kidneys into negative recipients in our program. We hope to incorporate this a standard practice for patients who consent to receive HCV + donor kidney.

We plan on using Sofosbuvir/Velpatasvir (Epclusa) as our first therapy choice. Our choice for Epclusa stems from the fact it's a daily one tablet preparation (improving patient's treatment adherence), has minimal drug-drug interaction with immunosuppressive drugs,

and is equally effective again all different HCV genotypes without needs for supplemental therapy. Epclusa has been studied in liver transplant patients and proven to be effective and very well tolerated (7). The one important caveat with Epclusa is its need for dose adjustment in renal failure. Hence, we plan on using Glecaprevir/Pibrentasvir (Mavyret) as agent of choice in patients who develop delayed graft function or continue to have poor allograft function with estimated glomerular filtration rate (eGFR) <30 ml/min by one to two weeks post-transplant. Mavyret does not require dose adjustment based on renal function and is equally effective against all different HCV genotypes. It was also studied in liver and kidney transplant patients and proven highly effective and well tolerated (8).

Sofosbuvir/Velpatasvir or elbasvir/grazoprevir will be used as a third-line drug based on the HCV genotype in case of coverage denial of the first and second-line drugs by the patient's health insurance.

**c. Significance:**

DAAs has the potential to turn HCV infection into a condition similar to cytomegalovirus (CMV) infection. Currently, it's a routine and completely acceptable practice to transplant organs from CMV+ donors to CMV- recipients. These recipients are at very high risk for CMV infection. In the absence of preventive measures, 40 to 100% off all kidney transplant patients will develop CMV infection and up to 67% will develop CMV disease that could be life threatening(14, 15). Such risk is greatly ameliorated by the presence of active treatment for CMV infection in the form of ganciclovir, cidofovir and foscarnet. Similarly, DAAs are effective and very well tolerated treatment that should make transplanting HCV positive organs into negative donors possible.

It is hard to accurately estimate the number of additional donors that could be available if HCV+ organs are being used routinely. It's estimated that between 2005 and 2014 about 4,144 kidneys from HCV+ donors were discarded(16). Many more kidneys from HCV infected donors were probably never procured because of fear of lack of appropriate recipients. Over 8000 lives could have been saved have these kidneys been utilized. Additionally, accepting kidneys from HCV+ donors can shorten patients waiting time on the deceased waiting list(17). This in turn results in improved survival and overall quality of life and decreased health care costs. A cost effectiveness analysis compared the cost associated with accepting HCV+ donor kidney followed by DAAs vs remaining on dialysis while awaiting for HCV- kidney found a total cost saving of about \$138,000 per patient(18).

We believe HCV positive donor organs are being underutilized in the current era of DAAs. We hope to provide further proof to the safety and utility of the strategy of transplanting HCV positive donor into negative recipient. We hope such proof will encourage transplant leaders, organ procurement organizations, and payers to invest into building an infrastructure that can turn such strategy into standard of care and ensure access and coverage for a variable selection of HCV therapies.

### **III. Procedures**

**a. Research design:**

This will be an open label, prospective, interventional, proof of concept study to evaluate the feasibility and safety of kidney transplant from HCV positive donors into HCV negative donor using Sofosbuvir/Velpatasvir as the preferred treatment choice for post-transplant HCV transmission.

The Ohio (OSUMC) has performed HCV+ into HCV- recipient liver transplants as standard of care since February of 2019. OSUMC has also been performing transplant of liver and kidneys from donors who are HCV antibody positive but PCR negative (non-viremic donors) since 2016. In order to present an overall picture of the patient outcomes across multiple types of organ transplants using HCV+ organs, we would like to review data from these liver and kidney transplant patients. To do so, retrospective data from recipients of HCV positive into negative liver transplants, and HCV antibody positive but PCR negative liver and kidney transplant recipients will be analyzed. Patients who were treated between January 19th, 2016 and November 26th, 2019 will be included in our analysis.

In order to confirm the safety of transplants using HCV+ kidneys, we will compare the outcomes of transplant from HCV viremic donors (HCV PCR+) to those from HCV non viremic donors (donors with HCV antibody neg/PCR negative and HCV antibody positive/PCR negative). To do so, we will retrospectively review charts of patients who received a kidney transplant at OSU between 1/1/2018 and 8/1/2020. This review will include recipients of HCV antibody negative/PCR negative (antibody (ab)-/Nucleic Antigen Test (NAT)-), HCV antibody positive/PCR negative (ab+/Nat-), and HCV antibody positive/PCR positive (ab+/Nat+).

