**b. Study sample:**

The study will aim to enroll 55 patients. Given the fact this is a proof of concept study, a sample size cannot be calculated based on power analysis.

Patients will be screened by a research nurse after completion of their pre-transplant evaluation. Patient who meets all inclusion and none of the exclusion criteria will be approached for consent. The consent will be discussed and explained to patient by a physician or research coordinator.

Inclusion criteria:

Adult age >18 years able to provide consent

Lack of available living donor

Calculated pre-transplant reactive panel (cPRA) of <80%

Estimated post-transplant survival (EPTS) index >20% and <80%

Negative pre-transplant HIV, HCV, and HBV serology and blood PCR

No clinically significant pre-transplant liver disease

Contraception based on the REMS protocol

Agree to abstinence from alcohol for at least 6 months post-transplant

Exclusion criteria:

Living donor available

Dialysis time >5 years

History of previous organ transplantation  
Listing for multi-organ transplantation  
Active or recent history (<6 months) of alcohol or substance abuse  
Clinically significant liver disease as determined by principal investigator  
History of hepatocarcinoma  
Pregnancy or lactation  
Refusal to accept blood transfusion  
HIV infection  
HCV pcr or antibody positive  
HBV infection  
Any condition that in the opinion of the investigator would impair the patients' ability to comply with the study procedures  
Donor selection criteria:  
Positive HCV PCR at time of donation  
KDPI<85%

For the retrospective chart review of HCV+ liver/HCV- recipients and HCV antibody positive/PCR negative liver and kidney transplant recipients, we aim to review 78 charts. The Ohio State University has so far performed 11 HCV+ into negative liver transplant, 25 HCV ab+/PCR negative kidney transplant and 25 HCV ab+/PCR negative liver transplant so far., Since this is a retrospective chart review portion of the study, a waiver of consent and HIPAA authorization will be requested for this portion of the study.

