**c. Measurements/End points:**

Primary efficacy end point is the proportion of patients with undetectable HCV PCR at 12 weeks after completion of HCV treatment with Sofosbuvir/Velpatasvir

Primary safety end point: The incidence of adverse events related to DAA treatment

Secondary end points:

eGFR and serum creatinine at 6 and 12 months post-transplant

Patient's survival at 6 and 12 months

Graft's survival at 12 months

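### The 2018–2020 kidney comparison meant to confirm safety limits its groups only by centre, organ, date and donor HCV status; no restriction, matching or adjustment is visible

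*Combined protocol and SAP*

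**What the plan says.** Section III.a (Research design) adds a retrospective comparison to the prospective study. Its purpose sentence begins "In order to confirm the safety of transplants using HCV+ kidneys, we will compare the outcomes of transplant from HCV viremic donors (HCV PCR" (cut here at the plus sign), and its population is given as "we will retrospectively review charts of patients who received a kidney transplant at OSU between 1/1/2018 and 8/1/2020". Three donor groups are named: ab-/NAT-, ab+/NAT- and ab+/NAT+. No other limit is stated, and the section does not say whether the ab+/NAT+ group is the trial cohort.

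Section III.b (Study sample) selects trial patients and donors much more narrowly. It requires "Lack of available living donor", cPRA below 80%, EPTS above 20% and below 80%, and "Negative pre-transplant HIV, HCV, and HBV serology and blood PCR". It excludes "Dialysis time >5 years", previous transplantation and multi-organ listing, and it limits donors to KDPI below 85%. Nothing extends these criteria to the chart-review groups.

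Section III.c names study end points including "eGFR and serum creatinine at 6 and 12 months post-transplant", patient survival and graft survival. III.a says only that outcomes will be compared.

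Section III.e describes a mostly descriptive analysis (medians with interquartile ranges, percentages) and treats any p-value below 0.05 as significant. Its item III opens with a gap, so further text may have stood there. Its one chart-review data list has demographics and dialysis time. It does not have KDPI, EPTS, cPRA, prior transplant, donor type (living or deceased), eGFR, creatinine, graft survival or patient survival.

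**The concern.** If the ab+/NAT+ group is largely the trial cohort, it was filtered on recipient and donor risk, while the comparators are whoever else received a kidney at the centre. As written, that includes living-donor, repeat and multi-organ recipients, highly sensitised patients, those with long dialysis and those given high-KDPI kidneys. The difference between groups then reflects these factors as well as viremia.

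The protocol itself names one such imbalance. Of HCV-infected donors, II.b (Rationale) says "These donors are usually young with fewer comorbid conditions such as diabetes and hypertension". That would favour HCV-positive kidneys. Living-donor recipients among the comparators could push the other way.

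A second problem would remain even with well-matched groups. Few graft losses are expected, so a p-value of 0.05 or more says little, yet the stated purpose is to confirm safety and the plan sets a significance threshold. The Significance section (II.c) hopes that the study's results will influence organ procurement organizations and payers.

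**Working it through.** The plan gives no sample size, event rate, margin or power for this comparison, so there is no figure to reproduce. The calculation below is an illustration.

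**Inputs.** From the documents: 55 patients to be enrolled and 25 ab+/PCR-negative kidney transplants (both III.b; the 25 were counted for the other chart review). Assumed: graft loss 6% in trial-type recipients; eGFR SD 18 mL/min; 150–300 comparators; 30–55 in the viremic group, because nothing says all 55 were transplanted by 8/1/2020.

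**Expected losses in the viremic group.** 55 × 0.06 = 3.3; 30 × 0.06 = 1.8. The exact (Clopper-Pearson) 95% interval for 3/55 is 1.1% to 15.1%.

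**Precision of a difference (95% half-width).** Graft loss: 1.96 × √[0.06 × 0.94 × (1/n₁ + 1/n₂)]. eGFR: 1.96 × 18 × √(1/n₁ + 1/n₂).

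**Power if viremic graft loss is doubled (12% vs 6%).** Two-sided Fisher exact test at 0.05, exact binomial enumeration, counting only a significant excess in the viremic group.

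| Viremic / comparator | Graft-loss half-width (points) | eGFR half-width (mL/min) | Power |
|---|---|---|---|
| 55 / 300 | 6.8 | 5.2 | 0.327 |
| 55 / 150 | 7.3 | 5.6 | 0.263 |
| 30 / 300 | 8.9 | 6.8 | 0.239 |
| 30 / 150 | 9.3 | 7.1 | 0.214 |

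Doubling from 4% gives power 0.249 (55/300) and 0.149 (30/150); doubling from 8% gives 0.419 and 0.261. Over the range 15–42%, a non-significant result is the more likely one even with doubled risk. The graft-loss half-widths use a normal approximation, which is rough with two or three events; the Fisher figures do not depend on it.

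**Case mix with no true viremia effect.** Comparators are split into living-donor, trial-eligible and outside-criteria recipients, with assumed graft loss of 2%, 6% and 12% and assumed eGFR of 65, 55 and 45. The viremic group is at 6% and 55.

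- Mix 40/50/10: 0.4×2 + 0.5×6 + 0.1×12 = 5.0%, so HCV-positive looks 1.0 point worse. eGFR: 0.4×65 + 0.5×55 + 0.1×45 = 58.0, so 3.0 mL/min worse.
- Mix 10/40/50: 0.1×2 + 0.4×6 + 0.5×12 = 8.6%, so 2.6 points better. eGFR: 0.1×65 + 0.4×55 + 0.5×45 = 51.0, so 4.0 mL/min better.

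All four differences lie inside the half-widths above.

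**The case against.** The strongest points on the other side are these.

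- **The absence coincides with a gap.** Item III of III.e opens with missing words, which may have described this comparison. This stands as a caution: the point can be made only about the visible text.
- **The analysis is called descriptive, and the plan never says non-significance will be read as safety.** That is true, and III.b disclaims a power basis. But a stated aim of confirming safety, alongside a 0.05 threshold, invites that reading, and a descriptive comparison still needs comparable groups.
- **Living donors may not be in the comparator.** The data list records donor cause of death, which presumes deceased donors. However, the list also has MELD and liver-disease etiology, so it may have been written for the 2016–2019 liver and kidney review; it does not settle the question. Without living donors the two mixes become (3.0 + 1.2)/0.6 = 7.0% and (2.4 + 6.0)/0.9 = 9.3%, so HCV-positive looks 1.0 to 3.3 points better. On eGFR it looks 1.7 to 5.6 mL/min better, and the top of that range reaches the narrowest half-widths. The direction therefore depends on the assumed mix.
- **If the ab+/NAT+ group is wider than the trial cohort, the contrast in selection weakens.** This is fair, and it is a reason to define the group.
- **Restriction is one choice among several.** Matching or a propensity score could also work. Restriction is preferred here because it serves every outcome without an outcome model built on two or three viremic-group losses.

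**Conclusion.** The concern holds. On the visible text, the comparison intended to confirm safety is crude: it does not align the groups on the factors by which trial recipients and donors were selected, and it does not plan to collect most of those factors. The size and direction of the resulting bias are unknown. The illustrated case-mix differences do not clearly exceed sampling error, and they rest wholly on assumed rates and mixes.

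The firmer result concerns inference. With 30–55 viremic-group recipients and a base graft-loss rate of 4–8%, a true doubling would be missed 58–85% of the time (1 − 0.42 to 1 − 0.15). A p-value of 0.05 or more would therefore not confirm safety, even with well-matched groups.

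The comparison is ancillary, both primary end points are unaffected, and fields can still be added to a retrospective review. This is a cheap improvement and does not threaten the trial.

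**What to change.** 1. **Define the groups (III.a).** State whether ab+/NAT+ means the trial cohort. Make the main comparison among transplants meeting the trial's chart-verifiable criteria: adult, deceased donor, KDPI <85%, EPTS >20% and <80%, cPRA <80%, dialysis not over 5 years, first kidney-only transplant, recipient negative for HIV, HBV and HCV. Say that the liver-disease, alcohol/substance and compliance criteria are not applied to comparators, since they rest on judgement or patient agreement. Show all-transplant figures only as context.
2. **Define the data (III.e).** Say which review the existing list serves. For this one, collect the selection variables above and the III.c outcomes: eGFR, creatinine, graft survival and patient survival.
3. **Define the analysis (III.e).** Tabulate baseline characteristics by group, including donor age, diabetes and hypertension. Report differences with 95% confidence intervals. Show eGFR unadjusted and adjusted for KDPI, EPTS and dialysis time. Report graft and patient survival without multi-covariate models. Describe the ab+/NAT- group without testing.
4. **Change the claim (III.a).** Replace the aim of confirming safety with a descriptive one, and state that p ≥ 0.05 will not be read as evidence of safety.

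**Cost.** Protocol and SAP wording, plus about eight selection items, two donor comorbidities and four outcomes per chart. Restriction shrinks the comparator: if 300 falls to 150 with 55 viremic, the half-widths go from 6.8 to 7.3 points and from 5.2 to 5.6 mL/min. The ab+/NAT- group suffers most. If 40–50% of the 25 qualified, 0.4 × 25 = 10 to 0.5 × 25 = 12.5 would remain; with 12 against 55 the same formulas give about 14.8 points and 11.2 mL/min, which is why that group is only described.

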**b. Study sample:**

The study will aim to enroll 55 patients. Given the fact this is a proof of concept study, a sample size cannot be calculated based on power analysis.

Patients will be screened by a research nurse after completion of their pre-transplant evaluation. Patient who meets all inclusion and none of the exclusion criteria will be approached for consent. The consent will be discussed and explained to patient by a physician or research coordinator.

Inclusion criteria:

Adult age >18 years able to provide consent

Lack of available living donor

Calculated pre-transplant reactive panel (cPRA) of <80%

Estimated post-transplant survival (EPTS) index >20% and <80%

Negative pre-transplant HIV, HCV, and HBV serology and blood PCR

No clinically significant pre-transplant liver disease

Contraception based on the REMS protocol

Agree to abstinence from alcohol for at least 6 months post-transplant

Exclusion criteria:

Living donor available

Dialysis time >5 years

History of previous organ transplantation  
Listing for multi-organ transplantation  
Active or recent history (<6 months) of alcohol or substance abuse  
Clinically significant liver disease as determined by principal investigator  
History of hepatocarcinoma  
Pregnancy or lactation  
Refusal to accept blood transfusion  
HIV infection  
HCV pcr or antibody positive  
HBV infection  
Any condition that in the opinion of the investigator would impair the patients' ability to comply with the study procedures  
Donor selection criteria:  
Positive HCV PCR at time of donation  
KDPI<85%

For the retrospective chart review of HCV+ liver/HCV- recipients and HCV antibody positive/PCR negative liver and kidney transplant recipients, we aim to review 78 charts. The Ohio State University has so far performed 11 HCV+ into negative liver transplant, 25 HCV ab+/PCR negative kidney transplant and 25 HCV ab+/PCR negative liver transplant so far., Since this is a retrospective chart review portion of the study, a waiver of consent and HIPAA authorization will be requested for this portion of the study.

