**d. Detailed study procedures:**

After completion of post-transplant evaluation and signing informed consent, patient status at UNOS will be changed to "Willing to accept HCV+ organ". Once an organ become available, it will be offered to the patients on HCV+ list per UNOS points system. Care following receiving HCV+ donor kidney for study patients will be as follow

1. Induction/maintenance therapy:

- I. Patient will receive induction with Thymoglobulin (rabbit ATG) for a total dose of 4-6 mg/kg per routine center protocol. Thymoglobulin induction will be started on day 0 after transplant surgery.
- II. Maintenance immunosuppressive therapy: patient enrolled in the study will receive the same routine maintenance immunosuppressive therapy used for recipients of HCV negative kidneys in our center. Maintenance

therapy will be started on post-operative day 1 with Tacrolimus, Mycophenolic acid, and rapid prednisone taper. Tacrolimus will be started at a weight based total dose of 0.15 mg/kg divided into two daily doses 12 hours apart. Trough levels will be checked daily prior to morning dose while inpatient and dose will be adjusted to target trough level of 8-12 for the first three months. Trough levels target in enrolled patients will follow our center post-transplant Tacrolimus trough target. Mycophenolic acid will be started at dose of 720 mg twice daily on post-Operative day one and continued long term. Dose can be adjusted/reduced per patient's primary transplant physician as appropriate due to side effect or infectious complications. Prednisone therapy will be tapered off by day 4 per center protocol

2. Hepatitis C evaluation and treatment:

- I. Recipients will have HCV PCR checked on admission day 0 prior to kidney transplant, and on day 3 prior to discharge. Patient with negative HCV PCR prior to discharge will have PCR checked weekly for 8 weeks then monthly up to 12 months post-transplant until PCR is positive. Checks will be stopped once PCR is positive. Patients with positive HCV PCR at day 3 post-transplant will not have further weekly or monthly checks but will follow the during treatment/post-treatment HCV PCR schedule mentioned below in section 2.3.d.
- II. Hepatology consult will be placed automatically on day 0 of transplant index admission and again if the patient is symptomatic for HCV.
- III. Direct acting anti-viral drugs (DAAs) will be initiated within eight weeks of first positive HCV PCR.

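### No prespecified rule pauses enrolment of 55 uninfected recipients of viremic-donor kidneys, although cure is read 24 to 32 weeks after first viremia and no earlier signal is tied to accrual

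*Combined protocol and SAP*

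**What the plan says.** Section III.a describes the trial: "This will be an open label, prospective, interventional, proof of concept study to evaluate the feasibility and safety of kidney transplant". Section III.b fixes the size ("The study will aim to enroll 55 patients") and adds that "a sample size cannot be calculated based on power analysis". Recipients must be free of infection at entry ("Negative pre-transplant HIV, HCV, and HBV serology and blood PCR") and donors must be viremic ("Positive HCV PCR at time of donation").

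Section II.b treats transmission as certain and rests its acceptability on treatment: "DAs are highly tolerated by patients and carry a cure rate of >95" per cent.

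The timing comes from three places. In III.d item 2, "Direct acting anti-viral drugs (DAAs) will be initiated within eight weeks of first positive HCV PCR". The same item sets 12 weeks of therapy for both the first-line and the second-line drug. Section III.c reads the outcome later still: "Primary efficacy end point is the proportion of patients with undetectable HCV PCR at 12 weeks after completion of HCV treatment".

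Earlier data are also collected. PCR is repeated at weeks 4 and 12 of therapy. Liver tests and clotting times are checked weekly for 12 weeks and then quarterly (III.d items 2 and 4). The primary safety end point is an incidence of DAA-related adverse events with no threshold, and III.e describes a mostly descriptive analysis. None of sections III.a to III.e contains an interim look, a pause or stopping criterion, a named safety reviewer or staggered accrual.

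**The concern.** The cure rate is the condition that makes it acceptable to infect these patients, but no enrolment decision depends on that rate holding at this centre. The primary outcome arrives months after exposure, so a sizeable part of the 55 could be transplanted before the first cure result is known.

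The prior evidence quoted in II.b does not fully stand in for a rule. The two kidney series of infected donors into uninfected recipients had 10 and 20 patients and used elbasvir-grazoprevir regimens, whereas this trial's first choice is sofosbuvir/velpatasvir. The protocol also foresees insurance refusal of the first- and second-line drugs. Timely DAA start is therefore a feasibility risk that the sponsor has itself identified, and it can be seen well before cure can.

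At stake is whether a run of uncured infections, late treatment starts or serious related events would prompt a planned review before more patients are exposed.

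**Working it through.** There is no plan figure to reproduce: 55 is stated without alpha, power or effect size.

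**1. Time to the cure result, from first positive PCR.** DAA start takes 0 to 8 weeks (III.d item 2), treatment 12 weeks (III.d), and the post-treatment wait 12 weeks (III.c).
- Shortest: 0 + 12 + 12 = 24 weeks.
- Longest: 8 + 12 + 12 = 32 weeks.
- Earlier signals: week-4 PCR at 4 to 12 weeks, week-12 PCR at 12 to 20 weeks, and a missed DAA start at 8 weeks.

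**2. Patients enrolled during that lag.** Accrual duration is not stated, so it is assumed, with even accrual. Number = 55 / (accrual weeks) × lag.
- 12 months: 55/52 × 24 = 25.4; 55/52 × 32 = 33.8.
- 18 months: 16.9 to 22.6.
- 24 months: 55/104 × 24 = 12.7; 55/104 × 32 = 16.9.
- 36 months: 8.5 to 11.3.

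**3. Operating characteristics of an illustrative non-cure rule.** Pause at 3 or more failures among the first 10 recipients with known outcome, 4 or more of 20, or 5 or more of 30. Exact sequential binomial, independent failures:

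| True failure rate | First crossed at 10 | At 20 | At 30 | Total |
|---|---|---|---|---|
| 5% | 0.012 | 0.011 | 0.007 | 0.029 |
| 10% | 0.070 | 0.083 | 0.069 | 0.22 |
| 20% | 0.322 | 0.288 | 0.166 | 0.78 |
| 30% | 0.617 | 0.283 | 0.074 | 0.97 |

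**4. Patients spared.** The totals above are chances of crossing a limit. When the nth outcome is known, about n + (patients enrolled during the lag) are already in. The expected number spared is the sum over looks of P(first crossed at that look) × max(0, 55 − n − enrolled during lag). At 20% failure:
- 12 months, 24-week lag: 0.322 × 19.6 + 0.288 × 9.6 + 0.166 × 0 = 9.1.
- 12 months, 32-week lag: 0.322 × 11.2 + 0.288 × 1.2 + 0.166 × 0 = about 4.
- 24 months, 24-week lag: 0.322 × 32.3 + 0.288 × 22.3 + 0.166 × 12.3 = 18.9.
- 24 months, 32-week lag: 0.322 × 28.1 + 0.288 × 18.1 + 0.166 × 8.1 = 15.6.

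This treats enrolment, transplant and first viremia as simultaneous and counts a pause as lasting. If enrolment resumes after review, fewer patients are spared.

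**5. Why late DAA start needs its own count.** The protocol's 95% is a cure rate, not a rate of cure plus timely start. If 5% are not cured and a different 5% start late (assumed), a combined count has 10% failure. The rule then pauses with probability 0.22 instead of 0.03, even though cure is as expected.

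**The case against.** The documents are silent on pausing; they do not say that accrual goes on regardless. A reader might infer that enrolment would continue whatever failures or liver harm appeared, or that the chance of a pause is zero. The text supports neither. The study is open label, so the investigator sees results as they arrive and could halt enrolment ad hoc, as could an IRB. The consent pages were removed and may describe oversight.

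A reader might also infer that nothing is known before 32 weeks. That is the ceiling, since DAA may start at any time within eight weeks, and PCR and liver tests report earlier. Nor does insurance refusal go unanswered: II.b and III.d provide alternative DAAs for the individual patient.

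Finally, the documents report cure in all 10 and all 20 recipients of the two earlier kidney series. They state no unacceptable failure rate, so any numerical limit is the reviewer's choice. The lag also means that the third look could not act at all with 12-month accrual.

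All of this stands, and it limits the size of the point. It does not supply a prespecified trigger. The earlier signals and alternative drugs serve individual care; none is linked to whether the next patient is enrolled.

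**Conclusion.** The point holds in a limited form. In the supplied text, nothing requires enrolment to pause if non-cure, late DAA start or serious related harm accumulates, although the justification for exposing 55 uninfected patients depends on cure. This is a gap in the design that should be closed; it is not a contradiction or a miscalculation.

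The benefit of closing it is real but moderate. The 78% crossing probability at 20% failure must not be read as 78% protection. The expected number spared is about 4 to 9 of 55 with 12-month accrual and 16 to 19 with 24 months. These figures rest on even accrual over an assumed duration, independent failures, illustrative limits and a lag of 24 to 32 weeks. A late-start tally and event-triggered pauses could act sooner; their effect has not been quantified here.

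**What to change.** Add one paragraph to III.b or III.c that governs accrual only, in two separate parts.

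1. **Safety and cure.** Pause enrolment for IRB review after any death, graft loss or liver failure judged related to HCV or to a DAA. Pause also on a running count of non-cure among recipients with known outcome. Limits such as 3 of 10, 4 of 20 and 5 of 30 are illustrative; the sponsor should derive its own from the failure rate it regards as unacceptable and state that rate.
2. **Feasibility.** Tally separately, with its own limit, infected recipients with no DAA started inside the protocol's eight-week window. This signal matures long before cure does.

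State the expected accrual duration, so that the number exposed at each look can be worked out. Enrolment resumes after review, and care of patients already transplanted is unchanged.

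The cost is the paragraph and a running tally of data already collected. No new committee is needed if the IRB does the review. The non-cure count carries about a 3% chance of a needless temporary pause if the 95% cure rate holds. Any pauses from part 2 and from related serious events come on top.
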